4.3.5 Electroencephalography (EEG) and Flanker Task

Electroencephalogram (EEG) recordings are performed using Bio-Semi (Amsterdam, The Netherlands) ActiveTwo electrode system with 64 scalp electrodes. Additional single active electrodes are attached on the outer canthus of each eye to record the horizontal electrooculogram (EOG) and infraorbitally and supraorbitally to the left eye to record the vertical EOG. Electrophysiologic signals are bandpass filtered at .01 to 67.0 Hz and digitized at 512 Hz.

In a modified version of the Erikson Flanker task subjects are required to respond as fast and accurate as possible according to the direction pointed by a centrally presented arrow with either the index finger of the left hand (<) or the right hand (>). Two additional arrows flanking the target arrow on the left as well as the right side either favored the target response (congruent trials, <<<< or >>>>) or primed the other response (incongruent trials, >><> or >>>>). The stimuli are presented on a black background for 650 ms. In order to assure a constant error rate throughout participants, the difficulty level during the task was programmed in a dynamical way. If an error is committed, the presentation time of the following stimulus will be prolonged by 20 ms. If there is a correct trial, presentation time will be shortened by 20 ms for the next trial. This should assure sufficient error trials and therefore ERNs for further evaluation. Furthermore, a feedback about the correctness of the response is given 3 seconds after response. In the case of a correct response a smiling face appears on the screen, if response is incorrect a sad face appears and if response is too slow, a question mark appears. In total 240 trials are presented randomized during 20 min. To counterbalance sequential effects each of the four stimuli follows every other stimulus with equal probability. To increase time-pressure, subjects are informed, that the absence of response will count as error and that they should respond as fast and accurate as possible.

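### The Flanker staircase's equal 20 ms steps balance only at 50% errors, which is chance in a two-choice task, so usable error trials for the EEG contrast may be scarce or diluted by guesses

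*Combined protocol and SAP*

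**What the plan says.** Section 4.3.5 of the combined protocol and SAP describes a left/right arrow task with congruent and incongruent flankers. On timing and length: "The stimuli are presented on a black background for 650 ms" and "In total 240 trials are presented randomized during 20 min". The difficulty is adapted "In order to assure a constant error rate throughout participants". After an error, "the presentation time of the following stimulus will be prolonged by 20 ms". Otherwise: "If there is a correct trial, presentation time will be shortened by 20 ms for the next trial". The stated benefit is: "This should assure sufficient error trials and therefore ERNs for further evaluation".

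Participants are also told that "the absence of response will count as error", and responses that are too slow get their own feedback symbol. The section gives no target error rate, no minimum or maximum presentation time, no mask and no response deadline. It does not say whether omissions and late responses move the staircase, or whether they enter the average for the error-related negativity (ERN).

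Section 4.1 lists brain activity measured by EEG among the primary outcome measures of PUK-GHB01, and section 8.1 includes brain activity in the primary endpoint.

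**The concern.** A staircase fixes the error rate through the ratio of its steps. Equal steps after every single trial aim at one error per correct response. With two response hands that is the rate a participant would reach without looking at the screen.

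An ERN analysis contrasts error trials with correct trials. It needs enough errors in which the wrong hand was pressed although the stimulus could be processed, and correct trials that were correct for a reason. A rule that aims at chance works against both needs. Either the stimulus becomes hard to see and the two trial types start to resemble each other, or the response window becomes so tight that many of the errors are not responses at all.

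**Working it through.** **Inputs, all from section 4.3.5.** Step after an error: +20 ms. Step after a correct trial: -20 ms. Starting time: 650 ms (taken as the start of the staircase). Trials: 240. Response options: two, so blind guessing gives 50% errors. No target rate is stated, so there is no planned figure to reproduce.

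**1. Balance point.** Expected change per trial is zero when up × p = down × (1 - p), where p is the error rate. Hence p = down/(up + down) = 20/(20 + 20) = 50%. This needs no model of the participant.

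**2. Speed.** At 90% correct the drift is 0.9 × (-20) + 0.1 × (+20) = -16 ms per trial. Then 650/16 is about 41 trials, so the rule takes effect early in a run of 240.

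**3. Bound.** Let E be errors and C correct trials, with E + C = 240. Presentation time after the run is 650 + 20(E - C). If it is never stopped by a lower limit and stays at or above zero, C - E is at most 32 (650/20 = 32.5). So E is at least (240 - 32)/2 = 104 trials, or 43%.

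**4. If presentation time limits visibility (simulation, assumed curves).** Errors come only from guessing at 50% when the arrow is not seen.
- Threshold 150 ms, slope 40 ms: about 44-46% errors in the last 120 trials with a minimum time of 0-20 ms, and about 35% with a 100 ms minimum. Mean time is about 48-72 ms with the 0-20 ms minimum.
- Exponential curves with a time constant of 30-100 ms: second-half errors of 37-41% with no minimum above zero, 22-36% with a 20 ms minimum and 2-18% with a 100 ms minimum.
- Lucky guesses under the first curve: at 45% errors another 45% of trials are guessed correctly, so 45/55 = 82% of correct trials are guesses. At 20% errors the share is 20/80 = 25%.

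**5. If presentation time is a response deadline (simulation, assumed).** Response time is normal with mean 400 ms and SD 80 ms; late or missing responses count as errors and move the staircase; 5, 10 or 20% of in-time responses use the wrong hand. Second-half errors are 50% and time settles near 405-428 ms. Of all 240 trials, 35-45% are late or missing, and only about 7, 14 or 31 are wrong-hand errors.

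**6. If presentation time has no effect (constant 10% errors).** Time falls to whatever minimum the program has and errors stay at 10%. The staircase then controls nothing.

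**7. Unequal steps.** +40/-20 ms gives 20/60 = 33%; +80/-20 ms gives 20/100 = 20%. With +80/-20 under the threshold curve of step 4 (minimum time 0-20 ms), late errors are about 19-20%, time is about 165-173 ms, and there are about 43 errors in 240 trials. Under the deadline model of step 5, wrong-hand errors rise from about 7/14/31 to about 10/22/47.

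**The case against.** The strongest reply is that a 50% balance point does not make the errors guesses. Incongruent flankers prime the wrong hand, participants work under time pressure, and omissions count as errors. If presentation time is a deadline, the arrow is visible for about 400 ms and the wrong-hand presses can be genuine flanker or speed errors. In the visibility simulation every error is a guess by construction, and this stays true under unequal steps; what improves there is the purity of the correct trials. A reader might infer that all error trials become guesses. The documents do not support that.

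Nor do they support three further inferences:
- That the error rate will in fact reach 50%. With an unstated minimum time it may settle well below.
- That any GHB effect is biased towards zero. Some dilution of the error-versus-correct contrast is plausible, but no calculation gives its size.
- That an accuracy outcome is lost. The plan names none for this task and intends a constant error rate.

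It is also fair to say that section 4.1 names EEG but not the Flanker task or the ERN, and that Table 4 gives the task no time slot. Unequal steps are no cure if presentation time has no effect on errors.

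What remains is that the step rule is stated, not merely incomplete. Its only balance point is chance, and each reading in which presentation time matters leaves the planned contrast weaker than it need be. Where it does not matter, the staircase does not control the error rate.

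**Conclusion.** The point holds in limited form. The equal-step rule aims at 50% errors, equal to two-choice chance, and this follows from the protocol's own figures. A large share of error trials may therefore be guesses, with many lucky guesses among the correct trials, or else late or missing responses. Which of these dominates depends on details that section 4.3.5 does not give.

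The size rests on assumed curves. It is about 35-45% late errors under the 150 ms threshold curve with a minimum time of 0-100 ms, and lower under some other curves with a minimum. Under the deadline reading it is 50% late errors, with about 7-31 wrong-hand errors of 240. The consequence for the GHB-placebo comparison cannot be quantified from the documents. This is a cheap design improvement worth making, confined to one EEG task.

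**What to change.** - Replace the equal steps with unequal ones and state the target error rate, for example +80/-20 ms (20%) or +40/-20 ms (33%).
- State a minimum and a maximum presentation time. The maximum matters: under the deadline model with 20% wrong-hand presses, +80/-20 ms let the time drift up to a median of about 950 ms.
- State the response deadline and keep it fixed, separate from presentation time.
- Let only wrong-hand errors and in-time correct responses move the staircase, and build the ERN error average from wrong-hand responses only. Count and report omissions and late responses separately by treatment. This depends on the fixed deadline. If the deadline shrank with presentation time, 10% wrong-hand presses would give 0.9 × (-20) + 0.1 × 80 = -10 ms per in-time trial, and the window would keep closing.
- Report the presentation time reached, by session and treatment, as the behavioural measure.

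The cost is a change of settings in the task script and a few sentences in section 4.3.5. There are two small downsides. If presentation time limits visibility, there are fewer error trials in total: in the last 120 trials about 24 (20%) instead of about 54 (45%). Also, section 4.2.1 says the neuropsychological tests have already been used in the group's trials, so a changed rule reduces comparability with that earlier work.

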4.3.6 Functional Magnetic Resonance Imaging (fMRI)

Functional Magnetic Resonance Imaging (fMRI) will be performed using the Philips Achieva 3.0 TX MR-System in the MR-Center of the University Hospital of Psychiatry Zurich. For functional imaging (fMRI), a T2*-weighted single-shot echoplanar sequence will be used in combination with an 8-channel head array (TE = 35 ms, TR = 3000 ms ($\theta = 82^\circ$), FOV = 220 mm, matrix = 80x80 reconstructed on 128 x128, voxel size: 2.75 x 2.75 x 4 mm, SENSE acceleration factor R = 2.0). Intrinsic functional connectivity at rest (Resting State [rs]-fMRI, 10 min), brain perfusion (Arterial Spin Labeling [ASL], 5 min) and brain anatomy (3D T1-weighted scan, 5 min) will be performed at baseline, followed by a post-Challenge Scan (rsfMRI/ASL: 12-15 min), an fMRI-Scan with the Sexual Arousal Task using the program Presentation® (Neurobehavioral Systems Neurobehavioral Systems, Inc. Albany, USA; 10-20 min) and a post-Task Scan (rsfMRI/ASL: 12-15 min). In the experimental nights 3+4 of PUK-GHB02, we will perform resting state fMRI/EEG scans.

4.3.7 Magnetic Resonance Spectroscopy (MRS)

A 2D J-resolved point-resolved MRS (JPRESS) will be used to investigate GHB induced metabolite alterations in the ACC. The method allows direct assessment of up to 18 brain metabolites (Fuchs et al., 2014) including myo-inositol, Glu, glutamine as well as Glu and GABA, as we and our associates have previously shown (Hulka et al., 2014, Walter et al., 2009, Northoff et al., 2007). Additionally, we are establishing a method to assess local GHB concentrations, which will be correlated with GHB plasma levels. Because of the smaller extension of the NAcc and the amygdala non-water suppressed MRS via the metabolite cycling technique (Hock et al., 2013) will be used. This method is optimally applicable for the metabolic profiling of the neurocircuitry of mood as shown for measurements of small brain volumes including NAcc and amygdala

(Hock et al., 2014b). In addition, 1D navigator acquisitions interleaved with MRS measurements will be used for real-time subject-motion detection, which has been shown feasible in MRS of human spinal cord (Hock et al., 2013), liver (Hock et al., 2014a) and heart muscle (Hock et al., 2015). Moreover, additional water scans will be acquired allowing absolute quantification by means of methods like ERETIC (Heinzer-Schweizer et al., 2010) which has been recently implemented for absolute metabolite determination using small MRS voxels (Zoelch et al., 2014).

MRS data will be acquired on our 3 T MR scanner equipped with related hardware as described above. Following a high resolution structural T1 weighted scan (acquisition time ca. 5 min) JPRESS measurements with acquisition parameters similar to (Hulka et al., 2014), of the ACC and non-water suppressed MRS of the NAcc and the amygdala similar to (Hock et al., 2014b) will be performed including navigator subject motion detection and absolute quantification. For MRS data quantification, Profit2 (Fuchs et al., 2014) JPRESS and LCModel, Version 6.3-1J [(Provencher, 1993), non-water suppressed MRS) will be used. After visual inspection of the acquired MRS data sets and evaluation of the navigator acquisitions to exclude data sets distorted by subject motion, Cramér-Rao lower bounds will be used to identify reliably quantified metabolites. In addition, signal to noise and line shape of the unsuppressed water peak will be used as quality criteria. All demographic, clinical, neuropsychological and MRS data, as well as correlations will be analyzed using SPSS® 22. We will use a combined MRS/EEG set up.

4.4 Anonymization

Anonymization will occur by means of a study code (see table 1, e.g. 112103: subject 11, experiment 2, experimental day 1, blood sample 3). Codes can be decoded through a list, which will be kept inaccessible for any other person than the principal- and the co-investigators.

Number	Significance
1 and 2	Study subject 01-32
3	Experiment 1 to 2
4	Experimental day 1 to 4
5 and 6	for all samples: chronological sample number 01-xx for all others: 00

Table 1 Description of the study code

4.5 Blood and other biosamples

4.5.1 Procedure

Experiment I: Every study subject takes part in at least two experimental sessions (GHB vs. placebo). An amount of blood of 150 ml (6 samples) will be taken by the principal investigator through an intravenous catheter during each session. For both sessions, a total amount of blood of 300 ml will be taken.

Experiment II: Every study subject takes part in four experimental sessions (2 x GHB vs. placebo), plus one preceding screening-night and one adaptation night anterior to each experimental night. A total amount of blood of 250 ml (18 samples, see 6.2) will be taken by a medical professional or a study nurse through an intravenous catheter during each session. Each sample will be tested for the quantities of the plasma markers IL-beta, IL-6, IL-10, TNF-alpha, CRP, IL-4, IL-18 und IFN-gamma, tryptophan, kynurenin, kynureninic

acid, neopterin, malondialdehyd, qinolinsäure, IDO (indolamine-2,3-deoxygenase) and substance P cortisol, progesterone, GHB, BDNF, FMRP, genetic markers, and prolactin. Moreover, other biosamples will be taken as follows: five hair samples (T0: before testing, T1: 2 days post-experimental night I, T2: seven days post-experimental night I, T3: two days post-experimental night II, T4: six weeks post-experimental night I, T5: before experimental night III, T6: the day after experimental night III, T7: the day after experimental night III), seven sweat samples (one sweat patch per night), four urine samples (after every adaptation and experimental night), nine nail samples (weekly nail clipping).

4.5.2 Anonymization of biosamples

Anonymization of the all samples will occur as described in 4.4. The two last numbers of the code signify the chronological sample number (01-xx).

4.5.3. Blood and other biosample analyses and conservation

The quantitative analyses of the samples for oxytocin, and ACTH will be made in the Laboratory for Biological and Personality Psychology of the Department of Psychology of the University of Freiburg ([name] - [name] - Germany). This happens in cooperation with and under supervision of Prof. [name], PhD.

The quantitative analyses of the samples for GHB, testosterone, prolactin, cortisol, progesterone, 3,5-THP und THDOC, the endocannabinoids and GHB will be made at the Institute for Biochemistry and Molecular medicine of the University of Bern ([name] - [name] - Switzerland). This happens in cooperation with and under supervision of Prof. [name], PhD.

The analyses of BDNF, FMRP, IL-beta, IL-6, IL-10, TNF-alpha, CRP, IL-4, IL-18 und IFN-gamma, tryptophan, kynurenin, kynureninic acid, neopterin, malondialdehyd, qinolinsäure, IDO (indolamine-2,3-deoxygenase), substance P and genetic markers will be made at the Institute for Pharmacology and Toxicology of the University of Zurich ([name], [name]). This happens in cooperation with and under supervision of Prof. [name], PhD.

The analyses of urine, sweat, hair, and nail samples will be made at the Institute for Forensic Medicine of the University of Zurich ([name], [name]). This happens in cooperation with and under supervision of Prof. [name].

The samples will be conserved in the locations of the analyses until the end of the study and then destroyed.

4.6 Drug accountability

4.6.1 Documentation of substance and application information's

Drug accountability is recorded via a separate document (Anlage 8o Drug Accountability). In this document, detailed information about the study substance (incl. charge number and expiry date) as well as the abstracted, applicated and potentially retracted or lost doses per patient. Every application is signed by both the blinded person who abstracts the drug or placebo and puts it into the application-cup and the principal investigator. Presuming an average subject weight of 70 kg, a total amount of 116 900 mg GHB (= 233 ml Xyrem oral solution) will be needed for the first, and 140000 mg GHB (= 140 ml Xyrem oral solution) for the second experiment. Four bottles of 180 ml Xyrem oral solution (= 90000 mg GHB each) will be purchased for

the study.

4.6.2 Drug labels

Every charge is labeled by the manufacturer with the trade name (Xyrem) and substance name (Sodium oxybate), content in mg and ml (90000 mg in 180 ml) and the expiry date, as requested by the Swissmedic. Additionally, we will label every charge with the study charge number, the project name and the name and telephone number of the principal investigator (see Table 2).

"Nur für klinischen Versuch!"	
Chargennummer	PUK-GHB01 / PUK-GHB02
Projekt	PUK-GHB01 / PUK-GHB02
Hauptprüfer / Ansprechpartner	[name] ([name]) / [name] ([name])

Table 2 Example for the additional study drug labels

4.7 Bias reduction

4.7.1 Placebo

We will use a double-blind, randomized crossover design for bias reduction. The investigator, monitor, the data analysts and the study subjects will be kept unaware of the treatment assignment. A placebo will serve as comparator.

4.7.2 Blinding procedure

Blinding will occur through a clinical staff member not involved otherwise in the study. This person will randomly abstract GHB (Xyrem) or placebo (0.9% saline solution) for each subject and put it into a plastic cup with 150 ml standard orange juice using a ml-syringe. In the first experiment (SocCog) sixteen subjects will receive 20 mg/kg and sixteen subjects 35 mg/kg GHB on one occasion and placebo on the other. For the MR-sessions, the same thirty-two subjects will receive 35 mg/kg GHB in one, placebo in the other session in a double-blind, randomized manner. In the second experiment 20 subjects will receive 50 mg/kg GHB on two occasions and placebo on two others. The information about the weight of the subject is transmitted anterior to this procedure. The cup is labeled with the study-code and will be kept back until the end of the study. When the cup is filled, it will be given to the principal investigator, who hands it out to the subject. The subject drinks the whole content and returns the empty cup to the principal investigator.

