4.1 Primary outcome measures

In the first part of the study (PUK-GHB01), plasma hormone levels, subjective effects assessed by questionnaires, and social cognition parameters assessed by specific computed test batteries, as well as brain activity assessed by electroencephalography (EEG) and functional magnet resonance imaging (fMRI) will serve as primary outcome measures. The results of the neuropsychological test battery performance will serve as longitudinal safety parameters to detect unexpected cognitive impairment after GHB intake. In the second part (PUK-GHB02), plasma hormone levels, GHB levels in plasma, urine, hair, and nails, sleep biomarkers such as brain-derived neurotrophic factor (BDNF), fragile x mental retardation protein (FMRP), IL-beta, IL-6, IL-10, TNF-alpha, CRP, IL-4, IL-18 und IFN-gamma, tryptophan, kynurenin, kynurenic acid, neopterin, malondialdehyd, qinolinsäure, IDO (indolamine-2,3-deoxygenase), substance P, and genetic markers, cognition, memory consolidation assessed by procedural and declarative memory tests, polysomnographic parameters, cerebral GHB-, GABA-, and Glu-concentrations in the ACC, Nacc, and amygdala, resting state connectivity, and measures of daytime sleepiness such as the Epworth Sleepiness

Scale (ESS), as well as subjective mood measures such as the Visual Analog Mood Scale (VAMS), and the Positive and Negative Affect Scale (PANAS) will serve as primary outcome measures.

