6.1 Outcome measures GHB01

Experiment	Method	Time (related to GHB application)
PUK-GHB01		
days	Cambridge neuropsychological automated test	t -40 min

1+2	battery (CANTAB) 1	
	GHB specific questionnaire (GSQ)	t -17, +38, +66, +106, +138 min, t+ 180 min
	Profile of Mood States (POMS)	t -13, +63, +141, +183 min
	Sexual arousal and desire questionnaire (SADI)	t -10, +51, +103, +160 min
	Visual Analog Scale (VAS)	t - 15 min, + 40, + 68, + 108, + 140, + 182 min
	Sexual Arousal Task	t + 41 min
	Movie for the Assessment of Social Cognition (MASC)	t +109 min
	Multifaceted empathy test (MET)	t +74 min
	Social Value Orientation (SVO)	t +90 min
	Charity Donation (CD)	t +69 min
	Reciprocity Task (RT)	t +163 min
	Social gaze test (SGT)	t +143 min
	Blood tests for endocrinology (BS-endo)	t-30 min, t0, t + 20 min, t + 35 min, t + 65 min, t +95 min, t + 124 min and t + 180 min
CANTAB 2	t >24 h	
days 3+4	Baseline-Scan	t - 30 min
	Post-Challenge Scan	t + 40-55 min
	SAT Task-related Scan	t + 60-80 min
	Post-Task Scan	t + 85-100 min

Table 4 Outcome measures GHB01: methods and time of testing

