8.1 Primary and secondary endpoints

The primary endpoint of PUK-GHB01/02 is the detection of alterations in brain activity, GHB-, GABA-, and Glu-concentrations, and blood parameters after the administration of GHB. The secondary endpoint of trial I is the correlation between serum hormone levels and neurocognitive as well as subjective measures. The secondary endpoint of trial II is the correlation of blood parameters with cognitive alterations as well as subjective measures and the correlation of cerebral GHB-, GABA-, and Glu-concentrations with results of the other experiments GHB01 and GHB02.

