8.3 Statistical analyses

We will use repeated measurements ANOVA for all dependent variables in both experiments.

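### The readable text states no balance of GHB-first and placebo-first order and names no period factor; a balanced order list and a period term are a cheap improvement

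*Combined protocol and SAP*

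**What the plan says.** Section 4.7.1 calls the trial a double-blind, randomised crossover. The mechanism is in 4.7.2, where a staff member not otherwise involved prepares the cup: "This person will randomly abstract GHB (Xyrem) or placebo (0.9% saline solution) for each subject". The same section fixes the dose groups of PUK-GHB01 at sixteen men each, gives all 32 men one GHB and one placebo MR session, and gives the 20 men of PUK-GHB02 two GHB and two placebo occasions. These rules fix dose and number of exposures. None fixes how many men receive GHB first.

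Section 8.3 is a single sentence: "We will use repeated measurements ANOVA for all dependent variables in both experiments". It names no factors. Section 8.5 excludes drop-outs and mentions no replacement.

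Timing of the outcomes (Table 4 in 6.1, and the flow chart in 6.2):

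- **GHB01 days 1+2.** The Sexual Arousal Task, charity donation, empathy test, social value orientation, social-cognition movie, social gaze and reciprocity tasks appear only after dosing, from t+41 to t+163 min.
- **GHB01 days 3+4.** The "SAT Task-related Scan" is post-dose only. Before dosing, according to 4.3.6, only rest, perfusion and "brain anatomy (3D T1-weighted scan, 5 min) will be performed at baseline".
- **GHB02.** The Iowa Gambling Task and delay discounting run only on the morning after dosing. Word pairs and finger tapping have a pre-dose run, and random number generation and psychomotor vigilance have adaptation-morning runs.

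Section 4.1 counts "social cognition parameters assessed by specific computed test batteries" and "cognition, memory consolidation assessed by procedural and declarative memory tests" among the primary outcome measures.

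**The concern.** In a two-session crossover, anything that differs between first and second session (practice, habituation, familiarity with the setting) is added to the GHB-placebo difference with one sign in GHB-first men and the opposite sign in placebo-first men. Even order makes these contributions cancel in the mean. A period term removes them from both the estimate and the error. The readable plan commits to neither.

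A same-session pre-dose measurement can absorb part of such a shift. The GHB01 days 1+2 social-cognition and neuroeconomic tasks and the two GHB02 morning tasks have none, so they depend most on order balance and on the model. At stake are a displaced estimate if the split happens to be uneven, and lost power if it is even but period is ignored.

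**Working it through.** **1. The plan's own figure.** Section 8.2 assumes d=0.7, two-sided 5%, 80% power, and states 19 subjects. For a paired t-test the noncentrality is d√n on n−1 df. At n=19 it is 0.7 × √19 = 3.05, power 82.3%. At n=18 it is 0.7 × √18 = 2.97, power 79.9%. The figure of 19 reproduces.

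**2. Model for the check.** Let D be a man's GHB-minus-placebo difference in units of its SD. Let π be the session-2-minus-session-1 shift. Then D = τ + π + e if GHB is second and D = τ − π + e if GHB is first, with e ~ N(0,1). *Assumptions:* an unrestricted 1:1 draw, and π = 0.25 or 0.5. The documents give no period effect.

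**3. How uneven the order can be** (exact binomial, p=0.5).

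| n | Exactly even | Uneven split, this or worse |
|---|---|---|
| 16 (one dose group) | 19.6% | 11:5, 21.0% |
| 20 (GHB02) | 17.6% | 13:7, 26.3% |
| 32 (GHB01 MR sessions) | 14.0% | 20:12, 21.5% |

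**4. Uneven split, no period term.** The estimate moves by π(n₁−n₂)/n. At 13:7 this is 0.25 × 6/20 = 0.075 SD or 0.5 × 6/20 = 0.15 SD. Type I error given the split, by simulation (at least 400,000 trials per cell):

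| Split | Shift at π=0.25 / 0.5 | Type I error |
|---|---|---|
| 11:5 | 0.094 / 0.188 SD | 5.8% / 7.5% |
| 13:7 | 0.075 / 0.15 SD | 5.5% / 6.5% |
| 20:12 | 0.0625 / 0.125 SD | 5.7% / 7.0% |

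Averaged over all draws, type I error is about 5% at each n.

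**5. Even split, no period term.** The estimate does not move, but the ±π goes into the error. The expected sample variance of D is 1 + π²n/(n−1). At n=20 and π=0.5 it is 1 + 0.25 × 20/19 = 1.26. The test becomes conservative (type I error about 3%) and power falls to 77%.

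**6. With a period term.** The estimate is the mean of the two order-group means, with variance ¼(1/n₁ + 1/n₂) and n−2 df. At 10:10 this is 1/20, as for the paired test. At 13:7 it is ¼(1/13 + 1/7) = 0.0549 against 0.05, about 10% more variance and no displacement from π.

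**7. Average power at d=0.7.**

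| n | No term, π=0.25 | No term, π=0.5 | Term, order left to chance | Term, balanced order |
|---|---|---|---|---|
| 16 | 72% | 65% | 71% | 74% |
| 20 | 82% | 76% | 82% | 84% |
| 32 | 96% | 93% | 96% | 97% |

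The last two columns do not depend on π. The 16-man group is below 80% under any order scheme; that shortfall comes from its size, not from order.

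**The case against.** The strongest reply is that randomisation already does its work. Order is random, so the estimate is unbiased and the test holds its level over repeated draws. That stands. A reader might infer from the missing balance that the GHB-placebo comparison is biased or invalid; the documents do not support this. Nor do they show that period is excluded from the analysis: 8.3 names no factor at all, so period is unspecified.

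The scheme may also be drawn where this review could not see it. Chart 1 is captioned as showing the order of sessions, 4.2.2 refers to it for the experimental nights, and Figure 1 is the GHB02 flow chart. Neither they nor the opening pages were available. This stands as a limit: the finding is about the readable text. The unrestricted draw is likewise an assumption, since 4.7.2 does not say how the draw is made.

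The size of the shift is assumed too. The text describes learning over trials within the Iowa task (4.3.4), not between sessions. At 0.25 SD, power with nothing changed is still 82% at n=20, above the planned 80%, and a period term without balanced order gains nothing there.

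Finally, a reader might take the task-related scan as proof that the endpoint in 8.1, "The primary endpoint of PUK-GHB01/02 is the detection of alterations in brain activity, GHB-, GABA-, and Glu-concentrations, and blood parameters", is highly exposed. It lacks a pre-dose run, but the same 32 men have already done the task on days 1 and 2, at least a week earlier, so it is less exposed. Spectroscopy, resting scans, and blood on GHB01 days 1+2 and GHB02 nights 1+2 have pre-dose measurements and are less exposed too.

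**Conclusion.** The point holds as a cheap improvement, not as a flaw that undermines the trial. Followed literally, the readable plan leaves order balance to chance and period outside the stated model. If sessions differ, the result is a displaced estimate given an uneven split, or lost power given an even one. The loss against balanced order plus a period term is about 1 to 2 points of power at a 0.25 SD shift. At 0.5 SD it is about 8 points at n=20 (76% against 84%), 9 in a 16-man dose group (65% against 74%) and 4 at N=32 (93% against 97%). At 0.5 SD the 20-man experiment falls below its own 80% target.

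These figures rest on the assumed shift and the assumed unrestricted draw. The outcomes most exposed are the GHB01 days 1+2 social-cognition and neuroeconomic tasks and the GHB02 Iowa Gambling and delay discounting tasks. Section 4.1 treats social cognition and cognition as primary and 8.1 does not name them; reconciling the two sections is a separate matter.

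**What to change.** **Section 4.7.2.** Replace the draw with a computer-generated order list made before the first subject and held by the staff member who prepares the cup. Balance it 8:8 within each GHB01 dose group for days 1+2 and 10:10 for GHB02 nights 1+2, with a separate balanced list for each MR session pair (GHB01 days 3+4, GHB02 nights 3+4). If Chart 1 or Figure 1 already shows a balanced order, repeat it here.

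**Section 8.3.** Fit treatment and period as fixed effects with subject as random factor in every GHB-placebo comparison. For GHB01 days 1+2 add dose group and treatment-by-dose group: a dose-group main effect alone would not address the dose-dependence aim in 2.2.1. The period term also protects the estimate if drop-outs disturb the balance.

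**Cost.** One list and one within-subject degree of freedom. If there is no period effect, power goes from 84.4% to 84.1% at n=20, from 97.0% to 96.9% at N=32, and from 74.5% to 74.0% in a 16-man group. With 19 men split 10:9 it is still 82%, so the sample size need not change.
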